## 5) Sample size

The sample size was determined based on power calculations on our primary outcome (HbA1c) and estimated attrition based on our previous studies in this population. Power calculations were based on standard deviations (SD) for changes in baseline to follow-up from our prior pilot study and assumed 80% power for a one-sided test at alpha of 0.05 corresponding to our hypothesis that the intervention would improve glycemic control and other outcomes. With the outcome of change in percent HbA1c from baseline to follow-up, using a SD of the change of 1.3937 for a minimum important difference of 0.5 in the change, the sample size needed is n=196 (n=98 in each of the two study arms). This sample size also provides 80% power for differences between arms in change in diabetes distress of 0.256 points, change in food insecurity of 1.3 points, and proportion at follow-up of 0.16 (e.g., 0.36 vs. 0.20) or greater for any binary outcome such hospitalization or emergency department visit. Anticipating attrition of 20%, the total sample size needed at recruitment would be at least 245. To be conservative, we enrolled 281 participants to account for the possibility of higher attrition than anticipated.

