For a secondary analysis, an intent-to-treat analysis will be performed using the Stata mixed procedure assessing whether the intervention resulted in differentially improved changes from baseline to six months in the primary outcome. The model will specify mixed (i.e., fixed and random) effects, be estimated by maximum likelihood, use all the longitudinal data, and account for variability among and within individuals using an exchangeable covariance structure. The fixed effects specified will be arm (intervention or control), visit (baseline or six months), and their interaction as a product term. The random effect will be individuals. The model is equivalent to a repeated-measures or differences-indifferences model. A fully fixed- effects model (with individuals as a fixed rather than random effect) will be examined as a robustness check.

Similar analyses will be done for the secondary outcomes using linear or logistic models as appropriate. For primary and secondary outcomes, Box-Cox transformations will be used to correct for skewness if needed.

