### 6) Additional analyses

- a) **Durability of health benefits:** To assess whether any improvements in primary, secondary, and intermediate outcomes were sustained in the intervention arm, researchers will estimate effects of the intervention on outcomes measured at 12 months. We will specifically assess the durability of HbA1c values and of the food security score from six months to twelve months in the intervention arm. For the intervention arm only, mixed models specifying two visit fixed effects will be used, one for differences between baseline and six months and one specifying differences between six and 12 months. The random effect will be individuals.

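### The three-visit durability model ties every visit contrast to one pooled within-person variance, so its 6-to-12-month confidence interval can be mis-stated in either direction

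*Combined protocol and SAP*

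**What the plan says.** Section 6, 6) Additional analyses, part a, restricts the durability analysis to the intervention arm, which has three visits (baseline, 6 and 12 months). There "mixed models specifying two visit fixed effects will be used", one for each successive interval, and "The random effect will be individuals". No residual structure and no robust standard error is named.

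The word exchangeable occurs only in Section 6, 2) Analysis methods, for the secondary two-arm, two-visit model, which will "account for variability among and within individuals using an exchangeable covariance structure". On its mean structure that section says: "The fixed effects specified will be arm (intervention or control), visit (baseline or six months), and their interaction as a product term". The plan itself calls this a difference-in-differences model. Its only robustness check replaces the random individual effect with a fixed one.

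The primary 6-month analysis is different: an ANCOVA of change on baseline value and arm. Section 4, 1) promises 95% intervals throughout. Section 6, 3) adds no further sensitivity analyses.

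**The concern.** A random intercept with independent, equal-variance residuals gives every visit the same variance and every pair of visits the same covariance. All three pairwise changes are therefore assigned one variance. With two visits this is harmless, because there is only one change to estimate. With three visits it is a real restriction.

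There is reason to doubt it here. Months 0 to 6 are the active intervention. Months 6 to 12 are a step-down to the food organisation's standard services (Section 3, Data collection). Spread of change need not be the same in both periods, and correlation often falls as visits lie further apart.

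This model is the only planned analysis of whether HbA1c and food security hold up after month 6, which is a stated hypothesis of Aim 3. Too wide an interval blurs a loss of benefit. Too narrow an interval overstates how well the 6-to-12-month change is known.

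Separately, the secondary two-arm model includes an arm effect at baseline, although randomisation makes the expected baseline means equal. That costs precision relative to ANCOVA.

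**Working it through.** **1. The plan's own figure.** Section 3, 5) Sample size "assumed 80% power for a one-sided test at alpha of 0.05", "using a SD of the change of 1.3937 for a minimum important difference of 0.5 in the change". Per arm, n = 2 × 1.3937² × (1.645 + 0.842)² / 0.5² ≈ 96.1, rounded up to 97, or 194 in total. The plan says "the sample size needed is n=196 (n=98 in each of the two study arms"), which agrees within two participants. Then 196 / 0.80 = 245, as stated: "Anticipating attrition of 20%, the total sample size needed at recruitment would be at least 245". So 1.3937 is an SD of change from baseline to follow-up. It is the only HbA1c variability figure in the documents.

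**2. Formula for three visits.** Write V06, V612 and V012 for the true variances of the three pairwise changes. With complete data, a random-intercept model estimates the variance of any change by their mean. Hence

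reported SE / true SE for 6 to 12 months = √[ (V06 + V612 + V012) / 3 / V612 ],

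and likewise for 0 to 6 months with V06 in the denominator. Each V is s_a² + s_b² − 2·r·s_a·s_b. Large-sample coverage of the 95% interval is 2Φ(1.96 × ratio) − 1.

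**3. Assumed patterns.** SDs are at 0/6/12 months; correlations are for 0–6 / 6–12 / 0–12.

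| SDs | Correlations | V06 | V612 | V012 | Mean | Ratio, 6–12 | Coverage, 6–12 | Ratio, 0–6 |
|---|---|---|---|---|---|---|---|---|
| 1.8/1.8/1.8 | 0.7/0.7/0.7 | 1.944 | 1.944 | 1.944 | 1.944 | 1.00 | 95% | 1.00 |
| 1.8/1.8/1.8 | 0.7/0.7/0.49 | 1.944 | 1.944 | 3.305 | 2.398 | 1.11 | 97% | 1.11 |
| 1.8/1.8/1.8 | 0.75/0.6/0.6 | 1.620 | 2.592 | 2.592 | 2.268 | 0.935 | 93% | 1.18 |
| 2.0/1.6/1.6 | 0.7/0.7/0.6 | 2.080 | 1.536 | 2.720 | 2.112 | 1.17 | 98% | 1.01 |
| 1.6/1.6/2.0 | 0.7/0.7/0.6 | 1.536 | 2.080 | 2.720 | 2.112 | 1.01 | 95% | 1.17 |
| 1.8/1.8/1.8 | 0.6/0.8/0.55 | 2.592 | 1.296 | 2.916 | 2.268 | 1.32 | 99% | 0.935 |
| 2.0/1.6/1.6 | 0.6/0.8/0.55 | 2.720 | 1.024 | 3.040 | 2.261 | 1.49 | over 99% | 0.91 |

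The first row is compound symmetry. In the first two rows √1.944 = 1.394, which matches the plan's SD of change. The other rows can be rescaled to match it without altering any ratio. The second row shows that the 6-to-12-month SE can be off even when V06 and V612 are equal, because V012 enters the average.

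Simulation with 125 participants (156 less an assumed 20%) gave coverage of 94.9%, 96.6%, 92.9%, 95.1% and 99.5% for rows 1, 2, 3, 5 and 7.

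**4. Scale in HbA1c points, n = 125.** Row 3: reported half-width 1.96 × √(2.268/125) = 0.264, true 1.96 × √(2.592/125) = 0.282. Row 4: reported 1.96 × √(2.112/125) = 0.255, true 1.96 × √(1.536/125) = 0.217.

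**5. Two-visit, two-arm model.** With equal SDs σ at both visits and correlation ρ, the interaction has variance proportional to 2σ²(1 − ρ). Baseline adjustment, or a common baseline mean, gives σ²(1 − ρ²). The SE ratio is √[2/(1 + ρ)]. From 1.3937² = 2σ²(1 − ρ), an assumed σ of 1.5 gives ρ ≈ 0.57 and σ of 2.2 gives ρ ≈ 0.80. The ratios are 1.129 and 1.054. At 125 versus 100 evaluable (156 and 125 less 20%), the SE is 1.3937 × √(1/125 + 1/100) = 0.187, against 0.166 at ρ = 0.57 and 0.177 at ρ = 0.80.

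In simulation the mixed-model interaction equalled the difference in mean change to rounding error. Mean SEs for mixed, change score and ANCOVA were 0.186, 0.186 and 0.173 (SDs 1.8 and 1.8, ρ 0.7), and 0.191, 0.192 and 0.144 (SDs 2.0 and 1.5, ρ 0.7).

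**The case against.** The strongest reply is that no error has been shown. The durability text names a random effect and is silent on the residuals, so exchangeability there is inferred. The documents give no 6-to-12-month SD, and under compound symmetry the interval is correct. The analysis is single-arm and additional, and significance testing is planned only if a journal requires it. All of this stands, and it limits the point to what can happen. The inference is still the ordinary reading, since a random intercept and nothing else yields that structure.

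A reader might infer several stronger things that the documents do not support:

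- **That the 6-to-12-month interval is too wide by a known amount.** Assumed change SDs (0–6, 6–12, 0–12) of 1.39/1.2/1.6 or 1.39/0.9/1.39 make the SE 17% or 39% too large. Only because the 6-to-12-month SD was set low do they point that way. Other plausible patterns give no error or too narrow an interval.
- **That equal variances cause the precision loss at 6 months.** They do not. With two visits and complete data the model's SE is the change-score SE. The loss comes from not using the baseline.
- **That the main 6-month result is affected.** It is not. The primary analysis is baseline-adjusted ANCOVA, chosen deliberately over mixed effects (Section 7).
- **That missed visits will bias the mixed model.** In simulation with 19% missed visits (156 versus 125, assumed SDs 2.0 and 1.6, ρ 0.7), bias was 0.001 when dropout depended on baseline alike in both arms. It was 0.026 when it did so in one arm only, and 0.06 when the dependence was opposite in the two arms.
- **That maximum likelihood must give way to REML.** At these sample sizes the SEs differ by less than 1%.

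**Conclusion.** The point holds as a conditional one of low severity. As written, the durability model lets one pooled variance set the interval for each visit contrast. The 6-to-12-month interval is then mis-stated whenever the variance of that change differs from the average of the three. Moderate assumed departures put the reported SE between about 6% too small and 17% too large (coverage about 93% to 98%). Stronger ones make it 30% or more too large. Neither the direction nor the size can be settled from the documents, and the closed form assumes complete data.

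The 6-month point is smaller: a 5% to 13% larger SE in a secondary analysis, assuming equal SDs of 1.5 to 2.2 at both visits. The simulated case with SDs of 2.0 and 1.5 shows that the gap from ANCOVA can be larger if the SD falls over follow-up. Free baseline means have no bearing on the single-arm durability model.

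**What to change.** In Section 6, 6) Additional analyses, state that the three-visit model uses an unstructured residual covariance across visits in place of the random intercept, or keep the random intercept and report robust standard errors. The unstructured form has six covariance parameters instead of two. Four more, with up to 156 participants, is a negligible cost, and the model stays valid if compound symmetry is true. It is a standard option of the Stata command already named for the secondary analysis.

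Optionally, in Section 6, 2) Analysis methods, drop the arm main effect from the secondary two-visit model so that both arms share a baseline mean, keeping visit and arm-by-visit. An unstructured covariance should go with it, so that the gain does not depend on equal SDs at the two visits. If the sponsor wants this model as a deliberate difference-in-differences check, one sentence saying so, and that it is expected to be less precise than the ANCOVA, is enough. Both changes are SAP wording only, with no new data and no effect on the primary analysis.

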**b. Analyses for Aim 2 (intermediate outcomes and mediation):**

The hypothesis is that the intervention will improve food insecurity (proximal intermediate outcome) and in turn nutrition (e.g., improved diet quality, BMI), mental health (e.g., less diabetes distress, depression) and health behaviors (e.g., medication adherence, diabetes self-management, clinic attendance) (distal intermediate outcomes) as suggested by our conceptual framework.

As described in Aim 1, analyses will be done for the intermediate outcomes using an analysis of covariance with linear or logistic models as appropriate. Statistical mediation from the intervention to the primary and secondary outcomes by the intermediate outcomes will be assessed first with the Stata sem procedure using traditional path analytic methods, testing for possible interactions between exposure (i.e., arm) and mediators, and then with Mplus using the causal inference method of Valeri and Vanderweele, which yields optimal estimates of indirect effects in the presence of non-continuous outcomes, interactions, and clustered data.

c. **Analyses for Aim 3 (cost-effectiveness analysis and process evaluation).**

To understand the relative value of CHEFS-DM in comparison to other health interventions, the incremental CE ratio (ICER) will be computed, defined by the difference in the per-capita intervention cost divided by the difference in the average intervention effectiveness.

The cost-effectiveness ratio is given by  $ICER = (\mu T - \mu C) / (\delta T - \delta C)$ , where  $\mu T$  is the per-capita cost of the treatment,  $\mu C$  is the per- capita cost of the control,  $\delta T$  is the health status of the treatment, and  $\delta C$  is the same measure for participants in the control group. To account for uncertainties in costs or effectiveness, estimates across a range of assumptions regarding future costs and health effects will be computed.

Confidence intervals for the ICER measures will be calculated using bootstrap methods. In terms of timeframe, the cost savings and health improvements at 6 and 12 months through direct measurement will be estimated. Additional analyses will be considered extrapolating cost savings to future periods under different assumptions of how long those changes last and impacts informed by the literature (e.g. the reduction in DM complications attributable to improved glycemic control).

Regarding process evaluation, a concurrent triangulation mixed methods process evaluation will be performed. Quantitative process evaluation data (structured interview and administrative data) and qualitative data (interviews and weekly team meetings) will be analyzed separately and then compared to cross-validate findings and generate lessons learned. Qualitative data analysis will be performed using content coding procedures to identify key themes using Dedoose software. Emergent themes will be identified and coded inductively. Coding consensus will be considered when transcripts achieve  $\geq 90$  percent coder agreement.

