## 2) Objectives

**Aim 1:** To determine the impact of CHEFS-DM on glycemic control and other cardiometabolic outcomes. The hypothesis is that CHEFS-DM will improve hemoglobin A1c (primary outcome), dyslipidemia, and health-related quality of life (HRQoL); blood pressure (BP) and acute care utilization; and improve diabetes medication adherence (secondary outcomes). Participants will be randomized to intervention versus control.. Data collection will include surveys, anthropometry, 24-hour dietary recalls, BP measures, medical record review, and blood draws. Characteristics of those most likely to benefit from CHEFS-DM will be described (e.g., poor T2DM control, gender).

**Aim 2:** To determine the impact of CHEFS-DM on intermediate outcomes that may mediate any impact of CHEFS-DM on T2DM health. Using our novel conceptual model, the hypothesis is that that CHEFS-DM will improve food insecurity (proximal intermediate outcome) which in turn will lead to improvements in nutritional (e.g., improved diet, body mass index), mental health (e.g., less diabetes distress, depression), and behavioral (e.g. improved medication adherence, diabetes self-management, and clinic attendance) paths (distal intermediate outcomes). Together these will improve T2DM control, cardiometabolic health, and HRQoL. Identifying the predominant causal paths will enable to further tailor the program to enhance impact during future implementation.

**Aim 3.** To determine the cost-effectiveness and sustainability of CHEFS-DM and obtain information to inform scale-up. a) The cost per quality-adjusted life year gained will be calculated; b) Whether any improvements in the intervention arm were sustained over 12 months of follow-up will be assessed; and c) A process evaluation will be performed, collecting qualitative and quantitative data with study participants and staff to determine what worked and did not work to guide future intervention scale-up efforts. The hypothesis is that the intervention may be cost-effective and possibly cost saving, and that health benefits will be sustained at 12 months.

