g) Qualitative interviews. In-depth, semi-structured interviews of 60-90 minutes will be conducted by UCSF RAs with up to 40 participants, including both completers and non-completers of the intervention. Most of these interviews will occur after the 6-month intensive phase of the intervention, with approximately 10 interviews at the end of 12 months. UCSF RAs will also interview up to 20 key informants including POH staff, study personnel, and clinicians from safety net clinics. Interviews will focus on mechanisms underlying program impacts, including possible nutritional, behavioral and mental health pathways. Other topics that will be asked during the interview are related to factors affecting program adherence and satisfaction, strengths and limitations of the CHEFS-DM intervention, barriers and facilitators to program participation, and suggestions for scale-up. The 12-month interviews will provide insight on experiences with transitioning to POH regular programming, and issues related to sustainability of any perceived impacts. Interviews will be conducted in English or Spanish by bilingual UCSF RAs, audio-recorded, and transcribed in the original language. The interviews will be conducted either over the phone and/or zoom or in-person, if able to do so per COVID-19 guidelines and based on the acceptability of meeting in-person among participants.

h) Administrative records from POH. POH will provide the following information:

- o Intervention costs incurred by POH. POH will provide administrative records of program expenditures to track all intervention costs, excluding research costs. These costs come from goods (the food and packaging), personnel, and fixed infrastructure and overhead.
- o Records of pick-up and/or receipt of delivered food. POH will provide administrative records of weekly pick-up and/or delivered food for each participant.

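### As defined, the cost-effectiveness ratio leaves out health-care cost offsets and is not expressed in QALYs, so it does not match Aim 3

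*Combined protocol and SAP*

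**What the plan says.** Section 2, 2) Objectives, Aim 3 commits to a specific measure: "The cost per quality-adjusted life year gained will be calculated". It adds the hypothesis that "the intervention may be cost-effective and possibly cost saving".

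Section 6, 2) Analysis methods, part c (Aim 3) gives the only working definition. The ICER is "defined by the difference in the per-capita intervention cost divided by the difference in the average intervention effectiveness". In the formula ICER = (μT − μC)/(δT − δC), μT "is the per-capita cost of the treatment" and δT "is the health status of the treatment", with matching terms for control. The same part says that "the cost savings and health improvements at 6 and 12 months through direct measurement will be estimated", that confidence intervals will be bootstrapped, and that costs and effects will be varied over a range of assumptions.

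On inputs, Section 3, Data collection, item h says: "POH will provide administrative records of program expenditures to track all intervention costs, excluding research costs". The interviews ask about hospital and emergency department use, and at 6 months about participants' own costs of taking part. Quality of life is measured with the SF-12v2, which Section 6, 1) Outcome definitions reports as T scores.

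**The concern.** An analyst who follows the Aim 3 analysis text to the letter would not produce the quantity that the Objectives promise. The numerator names intervention cost and no health-care cost. The denominator names neither QALYs nor a utility, and nothing in the plan converts the SF-12v2 to one. The estimate of cost savings stands beside the ratio, with no rule for bringing it in, no unit costs and no costing perspective.

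At stake is the headline economic result. A programme that lowered hospital use enough to pay for itself would still show a positive cost in the ratio. A ratio per unit of health status could not be set against other health interventions, which is the purpose that the section gives for it. And if these choices are left until the data are seen, the ratio can be chosen after the fact.

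**Working it through.** The plan states no ICER, cost, utility or QALY figure, so there is nothing to reproduce. The check is algebra on the plan's formula. All cost and utility values below are assumptions, used only to show sign and scale.

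**1. Numerator.** Under Section 3 (Control condition), controls are offered programme food only after 6 months. Section 4, 2) counts earlier receipt as a major violation. If cost means intervention cost, μC is therefore near zero and μT − μC ≈ C, the programme cost per person. If health-care cost is included and falls by S per person in the intervention arm, the net numerator is C − S.

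| Assumed C | Literal numerator | Net numerator, S from 0 to 5000 |
|---|---|---|
| 1000 | +1000 | +1000 to −4000 |
| 2000 | +2000 | +2000 to −3000 |
| 4000 | +4000 | +4000 to −1000 |

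Only the net form can turn negative. The literal form overstates net cost by exactly S (and understates it if use rises, S < 0).

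**2. Denominator.** Suppose that health status were a 0-1 utility, with equal arms at baseline and a difference D at 6 months (0.5 year).

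- Linear change: QALY difference = ½ × 0.5 × D = 0.25D.
- Full effect from the start: QALY difference = 0.5 × D = 0.5D.

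Dividing by D instead understates cost per QALY by a factor of 1/0.5 = 2 to 1/0.25 = 4. With C = 2000 and D = 0.03, the status ratio is 2000/0.03 ≈ 66,667. The cost per QALY is 2000/0.015 ≈ 133,333 (immediate effect) or 2000/0.0075 ≈ 266,667 (linear). With T scores, the result is a cost per T-score point and has no QALY reading.

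The two departures can pull in opposite directions: omitted savings make the ratio too high, and an unintegrated status difference makes it too low. The net direction cannot be predicted.

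**3. Baseline (illustration only).** The formula has no baseline term. With 156 and 125 participants (Section 7), the SE of a chance baseline difference in utility is SD × √(1/156 + 1/125) = SD × 0.120. For an assumed SD of 0.10, 0.12 or 0.15 this is 0.012, 0.014 or 0.018. A baseline imbalance of 0.02 would thus be about 1.1 to 1.7 SE (0.02/0.018 to 0.02/0.012), which is unremarkable. If it persisted in full, it would shift unadjusted 6-month QALYs by 0.02 × 0.5 = 0.01. If it had vanished by month 6, the shift would be ½ × 0.5 × 0.02 = 0.005.

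**4. Time horizon.** Section 3, Data collection follows controls for 6 months and the intervention arm for 12, and controls are then offered programme food. A between-arm difference in cost or QALYs is therefore directly measured only to month 6.

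**The case against.** The strongest reply is that the plan is under-specified, not wrong. The formula's own labels are broader than the sentence before it: cost of the treatment and cost of the control could include health care, and a control term would hardly be needed if only programme cost counted. Cost savings are explicitly to be estimated in the same paragraph. The Objectives name QALYs, so health status may be generic notation for them. The SF-12v2 is measured at baseline and 6 months and could supply a utility. Baseline-adjusted analysis is planned for the secondary outcomes, quality of life among them.

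Much of this stands. A reader might infer that the trial cannot show cost saving or cannot yield a cost per QALY. The documents do not support that: acute-care use and the SF-12v2 are both collected, and a savings estimate is planned. Nor does silence on baseline in the ICER paragraph amount to a plan for an unadjusted comparison. A reader might also take the 0.01 QALY shift to be as large as the likely treatment effect. The plan gives no expected utility effect, so that comparison cannot be made.

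What the reply does not remove is the defining sentence, which says intervention cost. No other text puts savings into the ratio, turns T scores into QALYs, or carries baseline adjustment into the ICER denominator. A definition with two readings, one of which can turn negative while the other cannot, needs to be settled in writing.

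**Conclusion.** The concern holds as a mismatch between the stated ratio and Aim 3. Taken literally, the ICER omits all health-care cost offsets and is not a cost per QALY. The numerator error equals the whole of any offset, whose size the documents do not allow one to estimate. The denominator error is a factor of 2 to 4 if health status is a utility with equal baselines and an effect between linear onset and immediate onset; with T scores the unit itself is wrong. The conclusion that the numerator stays positive rests on the literal reading of the defining sentence and on few controls receiving programme food before month 6. The baseline figures are only an illustration under an assumed utility SD of 0.10-0.15. The point affects Aim 3 and not the primary outcomes. It should be corrected before the economic analysis is run.

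**What to change.** Replace the ICER definition in Section 6, 2) c with one that states the following:

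- **Perspective and numerator:** the arm difference in programme cost plus self-reported emergency, urgent-care and hospital use multiplied by stated unit costs with their source.
- **Denominator:** the arm difference in QALYs from baseline to 6 months, from the SF-12v2 converted to a utility by a named algorithm (for example SF-6D) and integrated as area under the curve. Adjust for baseline utility by regression, in line with the baseline-adjusted models already planned for other outcomes.
- **Horizon:** the directly measured ICER stops at 6 months. Any 12-month ratio is labelled model-based, with the assumed course of the control arm stated.

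The cost is mainly SAP wording, but there are three drawbacks. Self-reported use adds variance to the cost difference. Section 7 says that record-based utilisation was dropped, so self-report cannot be checked against records. And Section 6, 1) reports acute care and hospitalisation as proportions with any use, so the team must confirm that the interview recorded numbers of events. If it did not, the plan should say how use will be priced and acknowledge the limitation.
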